 4. MBC
- 8 secondary cohorts:
 1. CRC (N=20),
 2. CRPC (N=20),
 3. ACC (N=50),
 4. Melanoma (N=50),

[figure not shown]
5. Mesothelioma (N=50),
 6. Urothelial carcinoma (N=50; note: enrollment is being stopped [N=44] due to the opening of a urothelial efficacy expansion cohort),
 7. Ovarian cancer (N=120), and
 8. Renal cell carcinoma (RCC), second line, (N=20 with expansion of 60 first-line).
- 4 efficacy expansion cohorts with the primary objective to assess BOR according to RECIST 1.1:
 1. Ovarian cancer, platinum refractory, prior liposomal doxorubicin (N=100);
 2. Urothelial carcinoma, platinum ineligible or progressed after at least 1 line of platinum-based therapy (N=200);
 3. Gastric and GEJ cancer, third line (N=150);
 4. HNSCC, platinum ineligible or progressed after at least 1 line of platinum-based therapy (N=150).

Subjects in the NSCLC (post platinum doublet), CRC, and CRPC cohorts will be enrolled in the USA only.

A schematic illustration of the trial design is shown in [Figure 5.1](#).

Figure 5.1 Schematic of Trial Design

Dose escalation (Standard “3 + 3” Design) up to 10 mg/kg

10 mg/kg once weekly safety evaluation cohort (N = 6)

Expansion cohorts in 16 different indications

- Dose and regimen will be defined based on dose escalation part
- Parallel enrollment
- 150 subjects per indication in primary cohorts
- 20-120 subjects per indication in secondary cohorts
- 100-200 subjects per efficacy cohort

Primary: NSCLC (post platinum doublet)*, NSCLC (first-line)*, gastric / GEJ cancer, and MBC

Secondary: CRC*, CRPC*, melanoma, ovarian cancer, ACC, mesothelioma, and urothelial carcinoma, RCC

Efficacy expansion: Ovarian (platinum refractory, liposomal doxorubicin), urothelial carcinoma (platinum ineligible, or progressed), gastric / GEJ (third-line), HNSCC (platinum ineligible, or progressed),

* Subjects in the NSCLC (post-platinum doublet), CRC and CRPC cohorts will be enrolled in the USA only.

Abbreviations: ACC: adrenocortical carcinoma; DLT: dose-limiting toxicity; CRC: colorectal cancer, CRPC: castrate-resistant prostate cancer; GEJ: gastroesophageal junction; HNSCC: head and neck squamous cell carcinoma; MBC: metastatic breast cancer; MTD: maximum tolerated dose; NSCLC: non-small cell lung cancer, RCC: renal cell carcinoma.

5.1.2 Trial Endpoints

5.1.2.1 Primary Endpoints

- Occurrence of DLTs during the first 3 weeks of treatment in the dose escalation part (excluding the once weekly 10 mg/kg cohort).
- The confirmed BOR, per RECIST 1.1, as adjudicated by an IERC (see Section 7.3) for subjects enrolled in the efficacy expansion cohorts only.

5.1.2.2 Secondary Endpoints

- Number, severity, and duration of TEAEs for all dose groups / indications according to the NCI-Common Terminology Criteria for Adverse Events (CTCAE) v4.0.
- Number, severity, and duration of treatment-related AEs according to NCI-CTCAE v4.0.
- PK profile.

- irBOR and BOR according to modified irRC and to RECIST 1.1, respectively, per investigator assessment.
- The confirmed BOR, per RECIST 1.1, as adjudicated by an IERC, for subjects enrolled in the secondary urothelial carcinoma cohort.
- irPFS time and PFS time according to modified irRC and to RECIST 1.1, respectively, per investigator assessment.
- OS time.
- Pharmacodynamic profile.
- Serum titers of anti-drug antibodies (ADA).
- Expression of PD-L1 on tumor tissue.
- For the primary expansion cohorts only: Unconfirmed response at Week 13 according to RECIST 1.1, per investigator assessment.
- Duration of response according to modified irRC and to RECIST 1.1, respectively, per investigator assessment.
- For the efficacy expansion cohorts only:
 - PFS time, according to RECIST 1.1, per IERC
 - Duration of response according to RECIST 1.1, per IERC.

5.1.3 Trial Medication Administration and Schedule

Subjects will receive i.v. infusion of avelumab (over 1 hour [-10 minutes / +20 minutes, i.e., 50 to 80 minutes]) once every 2 weeks. Premedication with an antihistamine and with paracetamol (acetaminophen) approximately 30 to 60 minutes prior to each dose of avelumab is mandatory (for example, 25-50 mg diphenhydramine and 500-650 mg paracetamol [acetaminophen] i.v. or oral equivalent). This regimen may be modified based on local treatment standards and guidelines, as appropriate.

For subjects in the 10 mg/kg once weekly cohort, subjects will receive i.v. infusion of avelumab (over 1 hour [-10 minutes / +20 minutes, i.e., 50 to 80 minutes]) once every week for the first 12 weeks, then starting with Week 13, once every 2 weeks thereafter. Premedication will be administered as above.

The trial treatment schedule is illustrated in [Appendix I](#).

The formulation and packaging information of avelumab is provided in Sections [6.1](#) and [6.6](#).

5.1.4 Avelumab Dose Escalation

5.1.4.1 Starting Dose

The starting dose of avelumab will be 1.0 mg/kg.

5.1.4.2 Dose Escalation Scheme

The avelumab dose escalation will be performed in cohorts of 3 subjects each according to the following dose levels with a 3 or 3.3 times of dose increase at each escalation:

- 1.0 mg/kg
- 3.0 mg/kg
- 10.0 mg/kg

[figure not shown]
The dose escalation criteria are as follows:

For each dose level, DLTs are assessed during the first 3 weeks. The criteria for moving from one dose level to another do not allow escalation to the next cohort in cases where ≥ 2 of 3 or 6 subjects in a cohort experience a DLT. If 1 of 3 subjects in a cohort experiences a DLT, this cohort will be expanded to 6 subjects. The MTD is defined as the highest dose where fewer than 2 of 6 subjects experience a DLT. Thus, the MTD cohort should accrue at a total of 6 subjects.

Once the MTD or maximum dose to be investigated is reached, the respective dose level cohort will be filled to a total of 6 subjects. Once the dose of 10 mg/kg is established as safe, 10 additional subjects at 3 mg/kg and 10 mg/kg each may be enrolled, for the purpose of generating additional safety, PK and receptor occupancy data, if agreed with the SMC.

A schematic of dose escalation is presented in [Figure 5.2](#).

Figure 5.2 Dose Escalation Algorithm for Doses up to 10 mg/kg

Abbreviations: IMP: investigational medicinal product; DLT: dose-limiting toxicity; MTD: maximum tolerated dose.

Each subject will stay on the dose level assigned at trial entry. The first subject of each cohort should be observed for 16 days (i.e., 48 hours after the second dose) for DLT occurrence before the second subject is to be administered the trial medication. Thereafter, within each cohort of the dose escalation phase, subjects may only be consecutively dosed with an interval of at least 48 hours. However, after 3 subjects have been treated at 10 mg/kg and no DLT has been observed, the other 3 subjects required to complete this cohort can be enrolled without sequential dosing (i.e., not required to wait until 48 hours). If no more than 1 DLT has been observed in these 6 subjects, the safety of 10 mg/kg will have been established.

At the conclusion of the DLT observation period of each cohort, a data review will be conducted. The SMC that includes all principal investigators is responsible for making dose escalation decisions. This committee will make the decision whether or not to escalate the avelumab dose to the next level by reviewing the safety data after all subjects of a cohort have completed Day 21 observation (the DLT evaluation period).

Once 1 subject has experienced DLT at a dose level below 10.0 mg/kg, dose escalation will be reduced as described in [Table 5.1](#):

Table 5.1 Modification of Dose Escalation Based on DLT Observations at Dose Levels Below 10.0 mg/kg

Dose Escalation Schedule Scenarios	Dose of Avelumab (mg/kg)		
	No DLT	DLT at Level 2	DLT at Level 1
Dose Levels			
Level 1	1.0	1.0	1.0
Level 2	3.0	3.0	1.5
Level 3	10.0	4.5	2.5
Level 4		7.0	3.5
Level 5		10.0	5.0
Level 6			7.5
Level 7			10.0

DLT: dose-limiting toxicity.

If > 1 out of 6 subjects experiences DLT at the first dose level, the SMC will discuss if an avelumab dose lower than the starting dose of 1.0 mg/kg will be tested. Other dose modifications (i.e., de-escalation) may also be considered by the SMC, if deemed necessary.

5.1.4.2.1 Dosing After 6 Subjects Treated at 10 mg/kg

Once the safety of the administration of the IMP at 10 mg/kg has been established in 6 subjects treated at 10 mg/kg and observed during the DLT observation period, subsequent dosing will be determined by the SMC after review of the safety and PK data generated for those 6 subjects.

If 1 DLT was observed in the 6 subjects treated at 10 mg/kg during the DLT observation period, a dose level of 15 mg/kg will be initiated. The safety, PK, receptor occupancy, and PD activity of the drug administered at a dose of 15 mg/kg will be evaluated using the methodology that was used for the other dose levels. If no subjects dosed at 15 mg/kg experience a DLT the next cohort can be dosed at 20 mg/kg. If 1 of 3 subjects dosed at 15 mg/kg experiences a DLT, this cohort will be expanded to 6 subjects.

Once the safety of PD-L1 has been established at 15 mg/kg (defined as no DLT observed in the 3 subjects or up to 1 DLT observed in 6 subjects treated at 15 mg/kg during the DLT observation period), the 20 mg/kg dose level will be initiated.

If there was no DLT observed in the first 6 subjects treated at a dose of 10 mg/kg, the dose escalation will proceed from 10 to 20 mg/kg. In this 20 mg/kg cohort, the safety, PK, receptor occupancy, and PD activity of the drug will also be evaluated using the methodology that was used for the other cohorts. Accrual in the 20 mg/kg cohort will be completed using a “3+3” method that was used for the completion of the previous cohorts.

[figure not shown]
After 3 subjects have been enrolled at a dose of 20 mg/kg and followed up during the DLT period, after the SMC has reviewed the safety data available and has concluded that no DLT occurred, 3 additional subjects will be enrolled at a dose of 20 mg/kg in an unstaggered fashion (i.e., 3 subjects the same day). If ≥ 2 (of 3 or 6) subjects experiences a DLT, the 15 mg/kg dose will have to be explored before the MTD can be determined.

Once the safety of a dose of 15 mg/kg or 20 mg/kg has been established (i.e., no more than 1 DLT out of 6 subjects treated at that dose), the SMC will have the possibility to allow enrollment of up to 15 additional subjects at that dose, without sequential dosing (i.e., not required to wait until 48 hours between 2 subjects). This additional cohort will have the purpose of generating safety, PK, and receptor occupancy data at a dose of 15 or 20 mg/kg.

Based on their review of the safety and PK data, the SMC will have the possibility to enroll an additional 10 subjects at 3 mg/kg and 10 mg/kg each.

A schematic of the dose escalation for 15 and 20 mg/kg is presented in [Figure 5.3](#).

Figure 5.3 Dose Escalation Algorithm for 15 and 20 mg/kg

Abbreviations: IMP: investigational medicinal product; DLT: dose-limiting toxicity; MTD: maximum tolerated dose.

5.1.4.2.2 10 mg/kg Once Weekly Cohort

With the safety of the 10 mg/kg and 20 mg/kg once every 2 weeks established, a new cohort of 10 mg/kg administered once weekly is being initiated in 6 evaluable subjects to assess safety of a more frequent dosing at 10 mg/kg every week for 12 weeks followed by 10 mg/kg every 2 weeks. Subjects in this cohort of 6 evaluable subjects will receive avelumab at 10 mg/kg once weekly for the first 12 weeks. Starting Week 13, dosing with 10 mg/kg will be once every 2 weeks. Overall safety of subjects in this cohort will be monitored by the SMC (see Section 2.2.1).

5.1.4.3 Dose-Limiting Toxicity

A DLT is defined as a \geq Grade 3 adverse drug reaction (ADR) according to the NCI-CTCAE v4.0, occurring in the DLT evaluation period of the dose escalation cohorts. ADRs are defined in this trial as any AEs suspected to be related to avelumab by the investigator and / or Sponsor.

The observation period for DLTs refers to the first 3 weeks of trial drug treatment in the dose escalation part for all dose cohorts for all subjects with data used for implementing the dose-escalation algorithm for determination of the MTD. Additional subjects enrolled in the dose escalation phase will have AEs collected but will not have a specific DLT observation period. A DLT is defined as any \geq Grade 3 treatment-related toxicity confirmed by the SMC to be relevant for the study drug treatment. The SMC recognizes that in the absence of prior human experience with avelumab, a conservative approach will be adopted in ascribing the relevance of the treatment-related toxicity to drug. Treatment-related SAE will be ascribed as related to drug except where a clear relationship to the underlying disease or recognized co-morbidities is evident. For this trial, the MTD is defined as the highest dose where < 2 of 6 subjects experience a DLT.

A DLT is specifically defined as any one of the following:

Any Grade ≥ 3 toxicity that is possibly, probably, or definitely related to avelumab, occurring during the DLT evaluation period (21 days after administration of avelumab), except for any of the following:

- Grade 3 infusion-related reaction resolving within 6 hours and controlled with medical management.
- Transient (≤ 6 hours) Grade 3 flu-like symptoms or fever, which is controlled with medical management.
- Transient (≤ 24 hours) Grade 3 fatigue, local reactions, headache, nausea, emesis that resolves to \leq Grade 1.
- Grade 3 diarrhea, Grade 3 skin toxicity, or Grade 3 liver function test (ALT, AST, or GGT) increase that resolves to \leq Grade 1 in less than 7 days after medical management (e.g., immunosuppressant treatment) has been initiated.
- Single laboratory values out of normal range that are unlikely related to trial treatment according to the investigator, do not have any clinical correlate, and resolve to \leq Grade 1 within 7 days with adequate medical management.
- Tumor flare phenomenon defined as local pain, irritation, or rash localized at sites of known or suspected tumor.

DLTs requiring treatment discontinuation are described in Section [5.1.7.2](#).

Subjects who do not complete the DLT observation period for reasons other than a DLT will be replaced.

5.1.5 Planned Number of Subjects

The planned number of the evaluable subjects for this trial is derived from the dose escalation “3+3” design and the expansion cohort sizes:

Dose escalation phase (including the 10 mg/kg once weekly cohort): 18 up to 66 subjects.

Primary and secondary expansion phase: 1040 subjects; 4 cohorts with 150 subjects each, 1 cohort with 120 subjects, 4 cohorts with 50 subjects, and 2 cohorts with 20 subjects each, and 1 cohort with 80 subjects (20 with expansion of an additional 60 subjects).

Efficacy expansion cohorts: 600 subjects; 2 cohorts with 150 subjects each and 1 cohort with 200 subjects and 1 cohort with 100 subjects.

The final sample size, however, may vary depending on the total number of dose levels to be escalated and tested, the subject replacement for DLT evaluations if applicable, and the number of expanded cohorts. At each dose level, 3 or 6 subjects will be treated depending on toxicities observed. A small number of additional subjects might be enrolled to replace the drop-out subjects.

In the event that rapid recruitment in the expansion phase impacts supply of IMP, the screening of new subjects for any cohort may be temporarily paused with 24 hours’ notice to investigators.

5.1.6 Planned Treatment Duration

The trial duration for a subject is estimated to be up to 30 weeks. This includes an 18-day screening period (decision will be made in this period for subjects’ trial inclusion if all eligibility criteria are met), a treatment duration until confirmed progression, unacceptable toxicity, or any criterion for withdrawal from the trial or IMP occurs (see Section 5.5) and an end-of-treatment visit 4 weeks after the last dose of avelumab administration.

For subjects who achieve a CR on avelumab therapy and then subsequently develop disease progression after stopping therapy, but prior to the end of the trial, one re-initiation of treatment at the same dose and schedule is allowed at the discretion of the investigator and agreement of the trial Medical Monitor. In order to be eligible for retreatment, the subject must not have experienced any toxicity that led to treatment discontinuation of the initial avelumab therapy. Prior to re-initiation of the study treatment, malignant disease needs to be radiologically re-staged to assess all known sites of the disease and to establish a new baseline for subsequent tumor measurements. Relevant safety laboratory results must be available and verified prior to re-initiating of treatment. Subjects who re-initiate treatment will stay on study and will be treated and monitored according to the protocol and the “until progression” schedule in the Schedule of Assessments (see [Appendix D](#)).

Moreover, any ADRs should be followed until they resolve, return to baseline, or are irreversible (see Section 7.1.4 for details).

Planned first subject in: Q1, 2013.

Planned date last subject out (dose escalation): Q2, 2018.

Planned date last subject out (after expansion and follow-up): Q2, 2019.

In the case of study termination (see Section 5.6), subjects continuing to benefit from study treatment may still have access to study treatment via enrollment in a rollover study if not available through some other mechanism (eg, expanded access, marketed product).

5.1.7 Dose Modification and ADRs Requiring Treatment Discontinuation

5.1.7.1 Dose Modification

In general, each subject will stay on the avelumab dose level assigned in the trial unless treatment needs to be stopped.

The dose of avelumab will be calculated based on the weight of the subject determined on the day prior to or the day of each drug administration.

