	
treatment are eligible) or immunodeficiencies.
 
10. Known severe hypersensitivity reactions to monoclonal antibodies (Grade \geq 3 NCI-CTCAE v4.0), any history of anaphylaxis, or uncontrolled asthma (i.e., 3 or more features of partly controlled asthma).11. Persisting toxicity related to prior therapy Grade $>$ 1 NCI-CTCAE v4.0, however sensory neuropathy \leq Grade 2 is acceptable.12. Pregnancy or breast feeding.13. Known alcohol or drug abuse.14. Clinically significant (i.e., active) cardiovascular disease: cerebral vascular accident/stroke ($<$ 6 months prior to enrollment), myocardial infarction ($<$ 6 months prior to enrollment), unstable angina, congestive heart failure (New York Heart Association Classification Class \geq II), or serious uncontrolled cardiac arrhythmia requiring medication.15. All other significant diseases (e.g., inflammatory bowel disease), which, in the opinion of the investigator, might impair the subject's tolerance of trial treatment.16. Any psychiatric condition that would prohibit the understanding or rendering of informed consent.17. Legal incapacity or limited legal capacity.18. Vaccination within 4 weeks of the first dose of avelumab and while on study is prohibited except for administration of inactivated vaccines (e.g. inactivated influenza vaccines).

Investigational Medicinal Product: dose/mode of administration/ dosing schedule
	
Avelumab will be administered as a 1-hour (-10 minutes / +20 minutes, i.e., 50-80 minutes) intravenous (i.v.) infusion. Subjects will receive avelumab once every 2 weeks until confirmed progression, unacceptable toxicity, or any criterion for withdrawal from the trial or IMP occurs (see Section 5.5). For the 10 mg/kg once weekly cohort only, subjects will receive avelumab once weekly for 12 consecutive weeks and then starting at Week 13, once every 2 weeks thereafter.
 
The dose of avelumab will be calculated based on the weight of the subject determined within 72 hours prior to administration. The dose of avelumab used for the previous administration can be repeated if the change in the subject's weight is 10% or less than the weight used for the last dose calculation.

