6.2 Dosage and Administration

Subjects will receive intravenous infusion of avelumab over 1 hour (-10 minutes / +20 minutes, i.e., 50 to 80 minutes) once every 2 weeks (for subjects in the 10 mg/kg once weekly cohort, once weekly for 12 weeks, then starting with Week 13, once every 2 weeks thereafter) (refer to [Appendix I](#)). Premedication with an antihistamine and with paracetamol (acetaminophen) approximately 30 to 60 minutes prior to each dose of avelumab is mandatory (for example, 25-50 mg diphenhydramine and 500-650 mg paracetamol [acetaminophen] i.v. or oral equivalent). This regimen may be modified based on local treatment standards and guidelines, as appropriate. Modifications of the infusion rate due to infusion-related reactions are described in [Section 6.5.4](#).

The starting dose of avelumab in the dose escalation phase is 1.0 mg/kg (dose-escalation according to 3 + 3 design up to 10.0 mg/kg is intended) and the treatment cycle will be 2 weeks (14 days). The dose of avelumab in the expansion phases is 10 mg/kg.

The dose of avelumab will be calculated based on the weight of the subject determined within 72 hours prior to administration. The dose of avelumab used for the previous administration can be repeated if the change in the subject's weight is 10% or less than the weight used for the last dose calculation. Subjects will receive avelumab until confirmed progression, unacceptable toxicity, or any criterion for withdrawal from the trial or IMP occurs (see [Section 5.5](#)). Subjects who have experienced a confirmed CR should be treated for a maximum of 24 months after confirmation, at the discretion of the investigator. If the investigator believes that a subject may benefit from treatment beyond 24 months, it may be permissible after discussion with the sponsor. Subjects who experienced a CR and have already stopped treatment can resume treatment with avelumab at the same dose and schedule. Subjects re-initiating treatment should be assessed according to the Schedule of Assessments ([Appendix I](#)).

In the case of study termination (see [Section 5.6](#)), subjects continuing to benefit from study treatment may still have access to study treatment via enrollment in a rollover study if not available through some other mechanism (eg, expanded access, marketed product).

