6.12 Treatment of Overdose

An overdose is defined as any dose 10% greater than the calculated dose for that particular administration. Any overdose must be recorded in the trial medication section of the CRF.

For monitoring purposes, any case of overdose, whether or not associated with an AE (serious or non-serious), must be reported to the Sponsor's Global Drug Safety department in an expedited manner using the Serious Adverse Event Report Form (see Section 7.4.1.4).

There are no known symptoms of avelumab overdose to date. The investigator should use his or her clinical judgment when treating an overdose of the investigational drug.

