Immunomonitoring (14)		X		X*		X		X				X	6-weekly up to incl. week 25	- /X					
Soluble factors (14)		X		X*		X		X				X	6-weekly up to incl. week 25	- /X					
Tumor biopsy or archived surgical	X								X					- /X					

CCI

ACTH: adrenocorticotropic hormone; ADA: anti-drug antibody; AE: adverse events; ANA: anti-nuclear antibody; ANCA: anti-neutrophil cytoplasmic antibody; β-HCG: β-human chorionic gonadotropin; CT: computer tomography; DLT: dose-limiting toxicity; ECG: electrocardiogram; ECOG: Eastern Cooperative Oncology Group; HBV: hepatitis B virus; HCV: hepatitis C virus; HIV: human immunodeficiency virus; IMP: investigational medicinal product; MRI: magnetic resonance imaging; PK: pharmacokinetics; RF: rheumatoid factor; SAE: serious adverse event; TSH: Thyroid-stimulating hormone, T4: Free thyroxine.

#Following approval of Protocol Amendment 7, the visits at Weeks 2 and 4 (Visit 4/Day 8 and Visit 6/Day 22) are no longer required and subjects will not be required to attend these visits.

*Sampling on Days 2 and 3 is optional. As a result, the visit at Day 2 is optional. However, the visit at Day 3 is required for all dose escalation subjects in order that relevant biomarker samples can be collected as described in the corresponding footnotes.

A time window of up to 3 days before or 1 day after the scheduled visit day (-3/+1 days) will be permitted for all study procedures (except Days 2 and 3), except for body weight, which should be obtained on the same day as study drug administration. In addition, the tumor evaluation (see Section 7.3) has a tumor assessment visiting time window of 5 days prior to dosing (-5 days).

1. Tumor evaluation at the end-of-treatment visit should only be performed if no disease progression was documented previously.
2. If another antineoplastic therapy is administered before the end of this 28 day-period, the end-of-treatment visit should be conducted if possible prior to the start of this new therapy.
3. Enrollment will be done after the confirmation of fulfilling all screening inclusion criteria (Section 5.3.1) without matching any exclusion criterion (Section 5.3.2).
4. 12-lead ECG should be assessed before infusion and 2 hours (\pm 20 minutes) after infusion.

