	
weeks until confirmed progression, unacceptable toxicity, or any criterion for withdrawal from the trial or IMP occurs.
 
The dose of avelumab will be calculated based on the weight of the subject determined on the day prior to or the day of each drug administration.
 
Premedication with an antihistamine and with paracetamol (acetaminophen) approximately 30 to 60 minutes prior to each dose of avelumab is mandatory (for example, 25-50 mg diphenhydramine and 500-650 mg paracetamol [acetaminophen] i.v. or oral equivalent). This regimen may be modified based on local treatment standards and guidelines, as appropriate.
 
Immediate access to intensive care unit or equivalent environment and appropriate medical therapy (including i.v. epinephrine, corticosteroids, antihistamines, bronchodilators, and oxygen) must be in place for use in the treatment of potential infusion-related reactions. Infusion of avelumab will be stopped in case of Grade ≥ 2 infusion-related, allergic, or anaphylactic reactions (according to NCI-CTCAE v4.0). Following avelumab infusions, subjects must be observed for 2 hours post infusion for potential infusion-related reactions.
 
Relevant clinical laboratory results essential for patient management decisions (hematology, biochemistry, liver function tests) must be available and reviewed before administration of avelumab.

Treatment and Trial Duration
	
The planned treatment duration is until unacceptable toxicity, or any criterion for withdrawal from the trial or IMP occurs.

Schedule of Visits
	
For dose escalation cohorts
 
 1. Screening (days -18 to first treatment) 2. Treatment phase 
Visits will take place on Days 1, 2, 3, 15, 29, 43, and every 2 weeks thereafter.
 
 3. Discontinuation visit and end-of-treatment visit 
All subjects who discontinue trial treatment prematurely for an AE should have a full safety evaluation at the time of discontinuation of trial treatment (discontinuation visit). In addition, all subjects will have an end-of-treatment visit scheduled 4 weeks after the last administration of avelumab but before any new therapy is started, if possible.
 
 4. Post-treatment follow-up

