
Trial Product
	
Avelumab will be administered as 1-hour intravenous (i.v.) infusion. Subjects will receive avelumab once every 2 weeks until confirmed progression, unacceptable toxicity, or any criterion for withdrawal from the trial or IMP occurs.
 
The dose of avelumab will be calculated based on the weight of the subject determined on the day of each drug administration.
 
Premedication with an antihistamine and with paracetamol (acetaminophen) approximately 30 to 60 minutes prior to each dose of

	
avelumab is mandatory (for example, 25-50 mg diphenhydramine and 500-650 mg paracetamol [acetaminophen] i.v. or oral equivalent). This regimen may be modified based on local treatment standards and guidelines, as appropriate.
 
Immediate access to intensive care unit or equivalent environment and appropriate medical therapy (including intravenous epinephrine, corticosteroids, antihistamines, bronchodilators, and oxygen) must be in place for use in the treatment of potential infusion reactions. Infusion of avelumab will be stopped in case of \geq Grade 2 infusion-related, allergic, or anaphylactic reactions (according to NCI-CTCAE v4.0). Following avelumab infusion, subjects must be observed for 2 hours post infusion for potential infusion-related reactions (IRRs).

Treatment and Trial Duration
	
The planned treatment duration is until unacceptable toxicity, or any criterion for withdrawal from the trial or IMP occurs.

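### Protocol 5.1.7.1 and 6.2 give conflicting dosing rules, and expansion SAP check PDEV16 lists some repeat doses that 6.2 permits as overdoses

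*Protocol*

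**What the plan says.** The protocol states the dosing-weight rule in more than one place.

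- **Section 5.1.7.1:** the dose is calculated from a weight "determined on the day prior to or the day of each drug administration". There is no allowance for repeating an earlier dose. The synopsis text on dose escalation points to this section for weight adaptations.
- **Section 6.2 and the synopsis entry on the investigational product:** the weight is one "determined within 72 hours prior to administration". Section 6.2 adds: "The dose of avelumab used for the previous administration can be repeated if the change in the subject's weight is 10% or less". The change is measured against the weight used for the last dose calculation.
- **Appendix I** (escalation, expansion and re-initiation schedules): procedures have a visit window, "except for body weight, which should be obtained on the same day as study drug administration". The once-weekly schedule has no such clause.
- **Section 6.12:** "An overdose is defined as any dose 10% greater than the calculated dose for that particular administration". It adds that "any case of overdose, whether or not associated with an AE (serious or non-serious), must be reported", in an expedited manner.

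The SAPs summarise the rule in their Section 6. The escalation SAP repeats the 5.1.7.1 wording ("weight of the subject determined on the day prior to or the day of each drug administration"). The expansion SAP says "determined on the day of each drug administration". Neither summary carries the 72-hour window or the repeat allowance.

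Expansion SAP Section 15 computes the actual dose level as the amount given divided by the last non-missing weight on or before the dosing day. It expresses each administration as a percentage of the planned mg/kg level. In its Appendix I, PDEV16 lists an overdose when the individual or cumulative relative dose intensity is 110 or more. Section 12.2.2 sends important deviations to a summary table and a listing.

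**The concern.** A site that repeats a dose after a small weight change follows 6.2 but departs from 5.1.7.1, which calls for a calculation at each administration. A site using a weight 60 hours old is in the same position. Both sections are current text, so a monitor cannot tell from the protocol which one governs.

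The conflict has a concrete result in the expansion SAP. PDEV16 compares the dose given with 10 mg/kg at the latest weight, not with the dose that 6.2 allows. A subject who has lost weight and receives a permitted repeat can therefore be recorded as overdosed. At stake are a single dosing rule for sites and an accurate deviation table.

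**Working it through.** **Inputs**

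- Planned dose in expansion: 10 mg/kg (protocol 6.2).
- Repeat permitted when the weight change is at most 10% of the weight last used for calculation (protocol 6.2).
- Actual dose level = dose given / latest weight; individual relative dose intensity = 100 × actual level / planned level (expansion SAP Section 15).
- Listing threshold: 110 or more (expansion SAP Appendix I, PDEV16).
- Dose-reduction flag: below 90% (expansion SAP Section 15).

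The plan gives no figure of its own to reproduce.

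**Formula.** Let W be the weight last used for calculation and L the fractional loss since then. The repeated dose is 10W mg and the current weight is W(1 − L). The actual level is 10/(1 − L) mg/kg, and the individual relative dose intensity is 100/(1 − L) per cent.

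**Where listing starts.** 100/(1 − L) ≥ 110 gives L ≥ 1 − 1/1.10 = 9.09%.

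**Where permission ends.** L = 10% gives 100/0.90 = 111.1%.

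The band that 6.2 permits and PDEV16 lists is therefore a loss of 9.09% to 10%, which is 0.91 percentage points wide.

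**Example: 700 mg repeated from 70 kg**

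| Current weight (kg) | Loss | Actual mg/kg | % of planned | Permitted by 6.2 | Listed by PDEV16 |
|---|---|---|---|---|---|
| 63.7 | 9.0% | 10.99 | 109.9 | yes | no |
| 63.6 | 9.14% | 11.006 | 110.06 | yes | yes |
| 63.35 | 9.5% | 11.05 | 110.5 | yes | yes |
| 63.0 | 10% | 11.11 | 111.1 | yes | yes |

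**Width in kilograms** (top of band W/1.1, bottom 0.9W)

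| Last dosing weight (kg) | Band (kg) | Width (kg) |
|---|---|---|
| 50 | 45.45 to 45.0 | 0.45 |
| 70 | 63.64 to 63.0 | 0.64 |
| 90 | 81.82 to 81.0 | 0.82 |

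**Weight gain.** A 10% gain gives 700/77 = 9.09 mg/kg, or 90.9%, which does not trigger the below-90% flag. The conflict arises only with weight loss.

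**Persistence.** Section 6.2 compares with the weight at the last calculation, not at the last visit. A subject who stays in the band can have each repeat listed.

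**The case against.** Several points on the other side carry weight.

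- **Timing.** A reader might infer four or five incompatible weight rules. There are only three: the escalation SAP matches 5.1.7.1, and the expansion SAP matches the same-day notes in Appendix I. They are also nested, since a same-day weight meets all three. The Appendix I notes say when weight is measured, not how a dose is calculated, so they are compatible with 6.2. What stands is the repeat allowance, which is in 6.2 and the synopsis and absent from 5.1.7.1, together with the narrower time window in 5.1.7.1.
- **Expedited reporting.** A reader might infer that a permitted repeat triggers the 6.12 duty, or that the duty is undetermined. The documents do not support that. Section 6.12 measures overdose against the dose calculated for that administration, and a repeat under 6.2 is most naturally that dose, so it exceeds it by nothing. Only 5.1.7.1 read alone suggests otherwise, and aligning that section removes the doubt.
- **PDEV16 as an exposure flag.** It refers to the assigned dose, cites neither 6.2 nor 6.12, and uses the SAP's own exposure measure. Flagging true exposure of 110% or more is a defensible safety measure. What stands is the label: an allowed dose is called an overdose and reported as an important deviation. Unlike most neighbouring rows, the PDEV16 check does not call for medical review that might filter such cases out.
- **SAP summaries.** These describe the trial and do not instruct sites. The escalation SAP (October 2015) cites Protocol Amendment 12, the expansion SAP is dated February 2017, and the protocol supplied is Amendment 18 of August 2018. The documents do not show when the 72-hour and repeat rule came in. Rewriting the escalation summary could misdescribe the rule its subjects were dosed under, and an undated PDEV16 exemption could hide deviations from an earlier, stricter rule.

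**Conclusion.** The point holds as a minor one. Section 5.1.7.1 conflicts with 6.2 and the synopsis within one protocol. As written, PDEV16 classes a permitted repeat after a 9.09% to 10% weight loss (110.0% to 111.1% of the planned dose) as an overdose and an important deviation.

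This assumes that the site repeats the dose instead of recalculating, that 6.2 was the rule in force at that administration, and that a current weight is in the database on or before the dosing day. The arithmetic is exact, but the frequency is unknown. The band is narrow, so few administrations may fall in it.

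The effect is confined to consistent dosing instructions and to deviation and overdose reporting. A reader might infer a threat to the trial's conclusions, but nothing here supports one. The full analysis set is defined by receipt of at least one dose, not by deviations, and the primary endpoint, alpha and power do not depend on PDEV16.

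**What to change.** 1. **Protocol 5.1.7.1:** replace the dosing-weight sentence with the 6.2 rule, or with a cross-reference to 6.2.
2. **Expansion SAP PDEV16:** exclude, or list under a separate label, repeats permitted by the dosing rule in force at the time of that administration. The date limit keeps departures from any earlier, stricter rule visible.
3. **Leave unchanged:** the relative dose intensity definition and the below-90% reduction flag, so that actual exposure of 110% or more still appears in the exposure outputs.

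A clause in 6.12 confirming that a repeat under 6.2 is the calculated dose would be helpful but is optional. The Appendix I notes and the escalation SAP summary need no change.

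The cost is one protocol sentence and one programming condition, plus establishing when the 6.2 rule took effect. No new data are collected. The change does not alter the dose variation that 6.2 itself allows.
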